	
P. vivax.
 
SSAT intervention is expected to reduce incidence of P. vivax in comparison to standard care. With the previous prevalence rate of 20%, we will have a power of >90% to detect a significant difference with the sample size of 350 children per group. We will anticipate the exclusion of 15% by recruiting 400 children per group.

Lay Summary
	
This study evaluates an experimental serological diagnostic technique intended to identify people at high risk of having dormant malaria parasites in their liver. The findings will assess the ability of this sero test to identify those carriers.
 
800 children living in eastern Indonesia will be individually randomised to the experimental serologic test or routine care.
 
Children in the serological diagnosis arm will be screened for the presence of antibodies to a previously validated panel of malaria antigens optimized for sensitivity to infection during the prior 9 months. Furthermore, they also will be screened by microscopy. If positive by either test, they will be treated for that malaria infection.
 
Children assigned to routine care will be screened by microscopic examination and treated when they show or have history of symptoms in the last 3 days.
 
After initial screening and treating according to diagnostic technique, all children will be actively followed for 9 months with PCR detection every 4 weeks.
 
During 9 month follow up, all children becoming acutely ill and proven to be positive for malaria by microscopy will be treated, in addition, all asymptomatic children will be treated at the final time point.
 
POC serology test will be performed at baseline and final timepoint on all children in both arms. The results from this POC serology test will not be used to inform diagnosis or treatment in any way at either of the timepoints.
 
None of these blood samples will be collected by venopuncture but instead minimally invasive lancet devices will be used.

Sero-diagnostic test
	
Quantitative measurement of antibody titres to a panel of 8 specially selected P. vivax antigens in study subject plasma samples using a Luminex MAGPIX® bead array system. This testing will be done at the Eijkman Institute in Jakarta. The results will be generated in no

	more than 7 days.
--	-------------------

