### **5.2. Secondary objectives:**

1. To evaluate the performance of a point-of-care (POC) anti-*P. vivax* antibody detection test relative to Luminex (MagPix).
2. To evaluate safety of high dose PQ administration in schoolchildren.
3. To evaluate the accuracy of Sahli's method and Standard G6PD (SD Biosensor Inc., Deogyong-daero, Korea) relative to HemoCue for haemoglobin measurement.

4. To estimate the sensitivity and specificity of a microscopic diagnosis of blood by sample from skin (ankle) relative to standard finger stick microscopic and PCR.
5. To measure duration of gametocyte in the blood samples of the skin of the ankle and finger prick.
6. To estimate the sensitivity and specificity of magneto-optical hemozoin detection by Gazelle® (Hemex Health, USA) relative to standard finger stick microscopic and PCR. To analyse hemoglobinopathies in schoolchildren using HemeChip by Gazelle (Hemex Health, USA)

*Primary endpoint:* the proportional reduction of *P. vivax* incidence by PCR in children serologically screened relative to those receiving routine care during 9 months of active follow-up.

*Secondary endpoints:*

- (I) Difference in the time-to recur of *P. vivax* by PCR in SSAT and control arms.
- (II) Difference in the number of recurrent *P. vivax* by PCR in SSAT vs. control arms.
- (III) Difference in the incidence of recurrent symptomatic *P. vivax* by LMF in SSAT vs control arms.
- (IV) Seroconversion rate before and after intervention in SSAT and control arms.
- (V) Sensitivity and specificity of POC antibody detection test vs. gold standard Luminex assay.
- (VI) Adverse event (AE) and Severe Adverse Event (SAE) of high dose PQ in schoolchildren.
- (VII) Hb level in Sahli's method, Standard G6PD (SD Biosensor Inc., Deogyong-daero, Korea), and Gazelle® (Hemex Health, USA), in comparison with HemoCue (HemoCue AB, Angelholm, Sweden).
- (VIII) Sensitivity and specificity of microscopic examination to detect parasitemia from the shallow skin vasculature of the ankle (light microscopy-skin/LMS) compared to standard microscopic (light microscopy-finger/LMF) and PCR.

- (IX) Mean duration time of gametocyte in LMS and LMF
- (X) Sensitivity and specificity of magneto-optical hemozoin detection (MOD) compared to standard malaria detection and PCR.
- (XI) Sensitivity and specificity of Standard G6PD (SD Biosensor, Inc., Deogyong-daero, Korea Korea) compared to CareStart G6PD RDT (Access Bio. Inc., New Jersey, USA).

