### 6.3. Study design and study overview

The study design is a randomized controlled trial with serological screening and treatment as the intervention. Selected schoolchildren will be allocated into two study arms: (1) serological screening and treatment (SSAT), and (2) routine care as control arm.

At enrolment, in the SSAT arm, individuals found *P. vivax* positive by either serological (Luminex) or Giemsa stained microscopic examination regardless of the symptoms will receive supervised treatment (direct observation) with high dose PQ (daily 1 mg/kg BW) for 7 days ( $P_o=P_v$ ). In the control arm, only symptomatic individuals found *P. vivax* positive by Giemsa stained microscopic examination will receive the same regimen ( $P_o=P_v$ ). In addition, in the treated children of both arms, dihydroartemisinin-piperaquine (DHA-PP) will be given as blood schizontocide according to body weight. All other species (*P. falciparum*, *P. malariae*) found by Giemsa stained microscopic examination will be treated according to national guideline. Serological examination will be performed by Luminex (done at Eijkman, Jakarta) and point-of-care (POC) antibody detection using rapid test on site

Follow up will be performed monthly for 9 months. During this period, 400  $\mu$ L of finger pricked blood samples will be collected from all children in both arms. These samples will be tested for malaria presence by PCR which will be done at EO CRU, Jakarta. However, children with clinical symptoms (body temperature of  $\geq 37.5^\circ\text{C}$  and/or history of fever within 3 days), will be examined by Giemsa stained microscopy on site, and treated if positive (any species) according to national guideline (unsupervised).

At the last follow up, a mass blood survey will be conducted to both arms for *Pv* serological test, LMF, and PCR. Those found positive by LMF for any species will be treated regardless of their symptoms.

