### **6.7. Follow up and end of study**

First follow up will be conducted one month after the last dose of PQ treatment administration. Every visit, blood samples from finger prick and skin (LMS) will be taken. Unlike in the 16ecurrent process, malaria blood smear will be made only from participants with clinical symptoms suggestive for malaria. If positive, they will be treated. All treatment during follow up period will be provided by PHC staff according to national guideline (Appendix B table 1 & 3).

At the end of study (month-9 of the follow up), mass blood survey will be conducted to collect finger prick blood (LMF, Pv serological test, qPCR) and LMS. Seroconversion will be assessed. All LMF (+) will be treated as above.

All study subjects will be followed until the end of study (month 9) although they cannot fulfil the complete schedule.

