### **6.8. Antimalarial treatment**

Treatment will be provided based on body weight (Appendix B). Blood schizonticide for any species is 3-day DHA-PP (daily dose: 6-10 kg=1/2 tab, 11-17 kg=1 tab, 18-30 kg=1 ½ tab, 31-40 kg=2 tab). For *P. vivax* subjects, the administration of high dose primaquine will be started at the same day of DHA-PP treatment (see Table 2 appendix B for PQ dosage). Meal should be given prior to PQ administration daily. The total dose of PQ should be completed within 10 days as the window period. Subjects who does not complete the dose will be recorded, and still be followed until end of study. Monitoring of Hb level and hemoglobinuria for treated subjects will be done daily before and during treatment by Hb measurement using HemoCue (HemoCue AB, Angelholm, Sweden) and urine test (inspection and urinalysis) in order to detect hemolysis. Primaquine will be stopped if hemolysis

occur, the subject will be observed for daily vital sign, Hb level, and urine until recovery. If worsen, the subject will be referred to the hospital for further management, and given blood transfusion if necessary (Appendix E).

Primaquine for *P. falciparum* will be given as single dose 0.25 mg/kgBW (6-17 kg=1/4 tab, 18-30 kg=1/2 tab, 31-40 kg=3/4 tab). *P. ovale* will be treated as *P. vivax*. Mixed infection with *Pv* will be treated as *Pv*.

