### **6.9. Adverse Event (AE) and Serious Adverse Event (SAE)**

Adverse events (AE) are defined as any untoward and unintended reaction during the study period. AE will be identified and recorded in CRF by field team in collaboration with the teachers and primary health center attendants. These subjects will be given symptomatic treatment as necessary. Specific AE are black urine, gastro intestinal disturbances, blue lips and breathless.

Serious adverse events (SAE) is an AE which becomes serious and could endanger the life of subjects, cause hospitalization/prolong hospitalization, and disability to conduct normal life. The SAE will be recorded in SAE form and reported to PI, clinician coinvestigators, Ethic Committee, and DSMB within 24 hours. SAE' subjects will be treated in RSPP/RS Atambua until recover completely. Complete SAE report will be distributed within one month after the occurrence of SAE.

The observation of AE and SAE will be performed routinely according to the schedule of drug administration (7 days).

If subject is allergic to DHA-PP, second-line treatment (7 days quinine) will be provided by the team in close collaboration with local primary health center (11-17 kg: 3x1, 18-33 kg: 3x1½, 34-40 kg: 3x2). All treatments for AE/SAE which will be given either at the PHC or in hospital, should be reported to the investigator team and being documented in the database.

Treatment will be stopped immediately if any of these following occurs: 1) allergy to the antimalarial regimen being given, 2) Hb drop of more than 20%, 3) active hemolysis which is proven by urine test and Hb drop, 4) Hb drop with warning sign of MetHb (breathless, blue lip/cyanosis, drowsiness, lethargy, palpitation), 5) Any possible SAE related to antimalarial treatment. Hospitalisation is indicated for 2) to 5).

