### 8.3. Data analysis

*Plasmodium vivax* incidence is defined as the total number of new genetically distinct *P. vivax* clones per child per detected during the follow up period. The analysis will use the comparison of two incidence rates between SSAT group and control group. For comparison, data will be entered as the number of recurrent *Pv* (numerators) and the total length of time people contributed in the cohort (person-time) as denominators. We will calculate the exact probabilities (Fisher's and Mid-P), the rate ratio with the exact confidence intervals and the measures of the impact of intervention. We will report the 95% of confidence interval for this comparison. Measures of the impact of intervention are computed for the prevented fractions in the exposed and in the population and the preventable fraction in the population.

As secondary endpoints, we will use Kaplan-Meier method to detect differences in the time-to-first recurrence of *Pv* by PCR in SSAT and control arms. The log-rank test is used to detect any difference between the two groups. Cox proportion hazard will be used to measure the effect size.

Multiple recurrences of *P. vivax* infections will be calculated during follow up. Number of events will be calculated, divided by the total length of time people

contributed in the cohort (person-time) as denominators. We will calculate the exact probabilities, rate ratio with the exact confidence intervals, and the measures of the impact of intervention using same tests as above.

Symptomatic recurrent *P. vivax* is defined as LMF positive with fever ( $\geq 37.5^{\circ}\text{C}$ ) or history of fever in the last 3 days during follow up. The same statistical test will be performed to compare both groups.

Difference of seropositivity between the two arms before and after the intervention will be calculated using chi-square test with p value  $< 0.05$  as limit of significance.

Sensitivity, specificity, positive predictive value, and negative predictive value of POC *Pv* antibody rapid test will be reported with Luminex as the golden standard.

Type and number of AE and SAE will recorded, and reported with total length of time people contributed in the cohort (person-time) as denominators.

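### AE/SAE of high-dose primaquine are to be reported over whole-cohort person-time, although routine AE observation covers only the drug course in treated children

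*Protocol*

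**What the plan says.** The safety endpoint in section 5.2 is "Adverse event (AE) and Severe Adverse Event (SAE) of high dose PQ in schoolchildren". For its analysis, section 8.3 says only that the type and number of AEs and SAEs will be recorded and "reported with total length of time people contributed in the cohort (person-time) as denominators". The same person-time wording is the denominator for *P. vivax* incidence earlier in that section.

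Section 6.9 states when events are looked for: "The observation of AE and SAE will be performed routinely according to the schedule of drug administration (7 days". The same section gives a wider definition: "Adverse events (AE) are defined as any untoward and unintended reaction during the study period".

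Cohort time is much longer than the drug course. Section 6.3 says "Follow up will be performed monthly for 9 months", and section 6.7 says "All study subjects will be followed until the end of study (month 9", including children who cannot complete the schedule. Under the synopsis, SSAT children negative by both serology and microscopy, and all controls except those who are symptomatic with *P. vivax* or *P. ovale* on the slide, receive no high-dose primaquine at enrolment.

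**The concern.** A rate is interpretable when its numerator and denominator cover the same children over the same time. Here the numerator comes mainly from treated children during a short, closely watched course. The denominator is everyone's follow-up. Untreated children and later months enter as event-free time, although nobody is scheduled to ask about events then.

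The safety objective concerns one regimen in schoolchildren, and section 4 says the evidence is to feed into guidelines for high-dose primaquine. A rate per cohort-year would look more reassuring than the data justify. It would also not be specific to that regimen: recurrences during follow-up are treated unsupervised under national guidelines, and Appendix B Table 3 gives a different, 14-day primaquine regimen for *P. vivax* and *P. ovale*. Events on that regimen would enter the same numerator.

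**Working it through.** The protocol states no AE rate or expected AE count, so there is no figure of its own to reproduce. The check has two parts.

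**1. What the forms and schedule collect.** In Appendix J, the complaint rows (nausea, vomiting, blue lips and so on) are on the treatment case report form, next to the daily tablet counts. The monthly follow-up form has date, weight, temperature, fever, LMF, LMS and qPCR, and no AE field. In Appendix H, haemoglobin checks after day 0 and all urine checks fall in the treatment week, and no AE assessment is listed for the monthly visits. This agrees with the 7-day sentence in section 6.9.

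**2. Size of the mismatch.** Inputs:
- Follow-up: 9 months = 9 × 365.25/12 = 273.9 days. The synopsis also says "all children will be actively followed for 9 months with PCR detection every 4 weeks"; nine 4-week intervals are 252 days.
- Observation window: 7 days (section 6.9). Alternatives are 10 days, since section 6.8 says "The total dose of PQ should be completed within 10 days as the window period", and 14 days, the number of day columns on the case report form.
- Children: 400 per arm.
- Share *s* of the SSAT arm treated: not given. I assume 30-70%, borrowing the seroprevalence range for school eligibility in section 6.2. Controls treated at enrolment are taken as about none.

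*Ratio of time denominators, treated children only* = follow-up days / window days:

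| Window | 273.9 days | 252 days |
|---|---|---|
| 7 days | 39.1 | 36.0 |
| 10 days | 27.4 | 25.2 |
| 14 days | 19.6 | 18.0 |

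*With untreated children included* (7-day window, 273.9 days):
- SSAT arm: 39.1/*s* = 55.9 at 70%, 78.3 at 50%, 130 at 30%.
- Both arms pooled: 39.1/(*s*/2) = 112 at 70%, 261 at 30%.

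*Dilution of a risk per child.* Most of the figures above come from comparing a week with nine months. Converting the reported rate back to a 9-month risk per child removes that part and leaves only the untreated children:
- SSAT arm: 1/*s* = 1/0.7 to 1/0.3 = 1.4 to 3.3.
- Both arms pooled: 2/*s* = 2/0.7 to 2/0.3 = 2.9 to 6.7.
- Treated children only: 1, that is, no dilution.

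*Illustration with invented counts:* 10 children with one event each among 200 treated of 400 in the SSAT arm.
- Per treated child: 10/200 = 5%.
- Per child-year observed on drug: 200 × 7/365.25 = 3.83 child-years; 10/3.83 = 2.6.
- Per child-year of SSAT-arm time: 400 × 0.75 = 300; 10/300 = 0.033. Over nine months this implies 0.033 × 0.75 = 2.5% per child, half of 5%.
- Per child-year of both arms: 10/600 = 0.017, implying 1.25% per child, a quarter of 5%.

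*If later events are also captured.* Suppose events off drug occur at 1/*k* of the on-drug rate and all are reported. For a treated child, the understatement of the on-drug rate is then 273.9/(7 + 266.9/*k*): 1.95 for *k* = 2, 4.5 for *k* = 5 and 8.1 for *k* = 10. The 39 is the limit in which no later events enter.

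**The case against.** The best defence is that section 6.9 defines AEs over the whole study period, involves teachers and health-centre staff in identifying them, and asks that treatment given for AEs and SAEs be reported to the team. On that reading the 7-day sentence says when observation is routine, not which events count, and cohort person-time is a coherent denominator for all AEs in the study. That stands for an all-cause study-wide rate. It does not make nine months of passive reporting equivalent to a week of supervised dosing, and it does not yield a rate for high-dose primaquine.

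It is also fair that the type and number of events are reported and that doses, dates and complaints are recorded per child. The risk per treated child could therefore be recovered, and an analysis plan not shown here may tabulate it. The endpoint is secondary and descriptive. The monitoring, stopping and SAE-reporting provisions do not use this denominator.

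A reader might infer that the primaquine event rate is understated 39-fold or more. The documents do not support this as a general statement. The figure is a ratio of time denominators. It falls to 18-36 for treated children under other readings of the protocol's own windows, and falls further if later events are captured. It is not a 39-fold error in the risk per child. Nor can all follow-up be called drug-free, since recurrences are treated.

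**Conclusion.** The mismatch is real and lies in the current text: the one pre-specified AE/SAE rate has a denominator that matches neither the children exposed to high-dose primaquine nor the time in which events are routinely sought. For the same event count, treated children's cohort time is about 39 times the 7-day course (18-36 under the alternative windows), and larger once untreated children are counted. As a risk per child the dilution is about 1.4-3.3-fold in the SSAT arm or 2.9-6.7-fold with both arms pooled.

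These figures assume nine months contributed by every child and essentially no treated controls. Those that include untreated children also rest on the assumed 30-70% treated share. The direction of the bias does not depend on these values, provided events are more frequent or better recorded on drug than off it. Severity: should-fix. The primary analysis is unaffected and the raw counts remain available.

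**What to change.** Replace the AE/SAE sentence in section 8.3 with the following:
- Report the number and percentage of children with each AE and SAE among those who took at least one dose, by regimen received, with exact 95% confidence intervals. Show the supervised 7-day high-dose primaquine course separately.
- If a rate is also wanted, use person-days from first dose to the end of AE observation, and state when that observation ends, since sections 6.8 and 6.9 and the case report form imply different lengths.
- List events reported outside that window separately, over follow-up time.

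The cost is a few lines of analysis text. Dates, daily tablet counts and complaints are already on the case report form, and treatment, visits and sample size do not change. The reported rates will be higher than under the present wording.

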*Plasmodium* gametocytes prevalence in LMF and LMS will be calculated as the number positive for gametocytes by each diagnostic method divided by the number of subject examined. Diagnostic performance will be derived using  $2 \times 2$  contingency to determine sensitivity, specificity, positive predictive value (PPV), negative predictive value (NPV). Results of qPCR detection will be used as the gold standard for diagnostic method evaluation. All statistics will be reported as absolute values with their 95% confidence interval (95% CI). To assess the significance of different results of LMF and LMS methods, we will apply McNemar's chi-square test on  $2 \times 2$  contingency tables derived from the results of each detection method.

We will evaluate durability analysis by measuring population half-life of the existence of *Plasmodium* gametocyte detected by LMS samples. Gametocyte prevalence-based approach will use data on the appearance and disappearance of any circulating gametocytes according to the prevalence at month 0 and the prevalence at the time when they are fully cleared from skin vasculature.

Sensitivity, specificity, positive predictive value, and negative predictive value of hemozoin detection will be reported using microscopic Giemsa examination as golden standard.

Hemoglobin measurement using Sahli method and Standard G6PD will be compared to HemoCue by t test.

Hemoglobinopathy rate will be reported as descriptive value.

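### The only LMS–LMF test in Protocol 8.3, McNemar with no split by qPCR written, compares overall positivity and not the sensitivity or specificity of endpoint VIII

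*Protocol*

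**What the plan says.** Objective 4 in Protocol 5.2 reads: "To estimate the sensitivity and specificity of a microscopic diagnosis of blood by sample from skin (ankle) relative to standard finger stick microscopic and PCR". Endpoint VIII is "Sensitivity and specificity of microscopic examination to detect parasitemia from the shallow skin vasculature of the ankle", "compared to standard microscopic (light microscopy-finger/LMF) and PCR".

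Section 8.3 treats the LMS data in three steps.

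- Gametocyte prevalence by each method "will be calculated as the number positive for gametocytes by each diagnostic method divided by the number of subject examined".
- Sensitivity, specificity, PPV and NPV from 2x2 tables, each with a 95% confidence interval. The reference is stated: "Results of qPCR detection will be used as the gold standard for diagnostic method evaluation".
- One comparative test: "To assess the significance of different results of LMF and LMS methods, we will apply McNemar's chi-square test", on 2x2 "contingency tables derived from the results of each detection method".

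The section does not say whether the McNemar tables hold all children or are divided by qPCR result. It gives no alpha, power or sample size for this comparison, and the protocol gives no expected sensitivity or specificity for either smear.

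**The concern.** McNemar's test on an LMS-by-LMF table asks whether the two methods are positive equally often. Endpoint VIII concerns two other quantities: how often each method is positive among infected children, and how often it is negative among uninfected ones. Without a split by the gold standard, the test adds the difference in true positives to the difference in false positives.

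Two errors of interpretation follow. A less specific ankle smear can give a significant excess of LMS positives with no gain in sensitivity. And an ankle smear that is both more sensitive and more specific can look no different from the finger smear, because the two differences cancel.

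Equal specificity cannot be taken for granted. LMS is a thin smear of ankle blood with parasites counted against red cells (7.1.2, 7.3), whereas LMF parasites are counted against leucocytes in a thick smear (7.3). What is at stake is the meaning of the one p-value attached to the LMS–LMF comparison. Neither the primary endpoint nor treatment is involved, since LMS results do not trigger treatment (6.10).

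**Working it through.** The protocol states no figure for this comparison, so there is nothing to reproduce. The check is how an all-pairs McNemar behaves beside one restricted to PCR-positive children.

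**Inputs**

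- From the protocol: PCR prevalence p = 20% (8.2; this is *P. vivax* in 2013, taken here as a stand-in for parasitaemia); N = 800 recruited, or 800 × 0.85 = 680 after the 15% exclusion in 8.2; LMS taken from all participants at enrolment (6.10).
- Assumed: all sensitivities (Se) and specificities (Sp); LMS and LMF results independent given PCR status; two-sided 5% level; uncorrected chi-square.

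**What the all-pairs test compares**

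Positivity of a method = p·Se + (1 − p)·(1 − Sp). The difference is p·(Se_LMS − Se_LMF) + (1 − p)·(Sp_LMF − Sp_LMS). At p = 20% the specificity gap has four times the weight of the sensitivity gap.

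**Formula**

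Let b be the expected LMS-only pairs and c the LMF-only pairs. Then z ≈ (b − c)/√(b + c), and the chance of a significant result favouring LMS is about P(Z > 1.96 − z).

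**Case A: equal sensitivity 30%, Sp 97% (LMS) v 99.5% (LMF), N = 800**

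- 160 PCR-positive: b = c = 160 × 0.30 × 0.70 = 33.6.
- 640 PCR-negative: b = 640 × 0.03 × 0.995 = 19.1; c = 640 × 0.005 × 0.97 = 3.1.
- All pairs: z = 16.0/√(67.2 + 22.2) = 16.0/9.46 = 1.69, so about 39% favour LMS. Simulation with 100,000 replicates gives 40%.
- PCR-positive pairs only: z = 0, so 2.5% favour LMS.

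At N = 680 (136 positive, 544 negative): z = 13.6/√(57.1 + 18.9) = 1.56, about 34%; simulation gives 35%.

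**Case A, other LMS specificities (simulated, N = 800)**

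| LMS specificity (LMF 99.5%) | All-pairs test favours LMS |
|---|---|
| 99.5% | 2.5% |
| 99% | 5.6% |
| 98% | 18% |
| 97% | 40% |
| 95% | 82% |

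At LMS specificity 97%, varying prevalence over 10–30%, sensitivity over 30–50% and N over 700–800, the figure runs from 20% to 66%. Within PCR-positives it stays at about 2.5% throughout.

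**Case B: LMS better on both, Se 42% v 30%, Sp 99.5% v 97%, N = 800**

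- PCR-positive: b = 160 × 0.42 × 0.70 = 47.0; c = 160 × 0.58 × 0.30 = 27.8; z = 19.2/√74.9 = 2.22, so about 60% detect the gain.
- All pairs: the negatives contribute −16.0, so z = 3.2/√97.1 = 0.32, about 5%.

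**Case C: real gain, Se 45% v 30%, both specificities 99.5%, N = 800**

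Simulated power is 76% on all pairs and 79% on PCR-positive pairs. The two tests nearly agree.

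**Dependence.** If the two smears tend to agree given PCR status, b − c is unchanged and b + c shrinks, so z grows in size. Independence therefore does not exaggerate Case A.

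**The case against.** The strongest defence is that 8.3 does little wrong as written, and much of it stands.

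- A reader might infer that the protocol orders McNemar on all pairs whatever the PCR result. It does not say so. The plain reading follows from tables built on the two methods' results, but the population is unstated, and a SAP not seen here may settle it.
- A reader might infer that extra ankle positives will be counted as better detection. The text speaks only of different results and ties no superiority claim to the p-value. The skin-reservoir hypothesis in section 4 makes that interpretation likely, but it remains an inference.
- A reader might infer that sensitivity is left unexamined. It is not: the objective is to estimate, and each method's sensitivity and specificity are reported against qPCR with 95% intervals. Excess LMS false positives would appear there as lower specificity. The remaining gap is that separate intervals ignore the pairing, while the one paired test answers another question.
- All-pairs McNemar is a valid comparison of the gametocyte prevalences defined in the same part of 8.3.
- Cases A and B rest on assumed specificity gaps; Case C shows that without a gap little is lost.
- A reader might also class every LMS-positive, LMF-negative, qPCR-negative child as a false positive. The documents do not support that. The qPCR uses finger-prick blood (6.3, 7.2), targets 18S rRNA and not a gametocyte stage (7.8), and section 4 hypothesises that gametocytes are held in the skin.

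**Conclusion.** The point holds in limited form. Section 8.3 names qPCR as the gold standard, yet its only LMS–LMF test carries no qPCR split. Read plainly, that test compares positivity, so it tests neither the sensitivity nor the specificity difference that endpoint VIII invites.

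The distortion ranges from negligible, with equal and high specificities, to about 35–40% of trials wrongly favouring LMS under the assumed 97% v 99.5%. In the offsetting case, detection of a real gain falls to about 5%, against about 60% within PCR-positives. These sizes depend on assumed accuracies; the direction of the effect does not. The point is minor: it concerns a secondary diagnostic endpoint, the accuracy estimates are planned anyway, and the primary comparison is untouched.

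**What to change.** In 8.3, state which pairs enter McNemar's test:

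1. For parasitaemia (endpoint VIII), run exact McNemar within qPCR-positive pairs for sensitivity and, separately, within qPCR-negative pairs for specificity. Give each paired difference with its 95% confidence interval.
2. Keep any all-pairs McNemar only as a labelled comparison of positivity or of gametocyte prevalence.
3. Report LMS-positive, LMF-negative, qPCR-negative children as a separate row, without deciding in advance whether they are false positives or skin-held infections.

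The cost is a few lines of text and no new samples. The drawback is a smaller base for the sensitivity test: about 0.20 × 680 = 136 to 0.20 × 800 = 160 children if prevalence is near 20%. The exact test is also slightly more conservative than the chi-square used in the figures above. The split does not answer the question of gametocyte sensitivity, because the qPCR is not stage-specific.
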